6.3.1.6.2 Skin Rash (other than e.g. SJS, TEN, DRESS)

For skin rash of mild/moderate severity (defined as those causing minimal symptoms which require no or minimal supportive treatment), deferasirox drug should be continued without dose adjustment. The skin rash may resolve spontaneously without further intervention.

If the rash persists for >1 week or becomes more severe, treatment with deferasirox will be interrupted. After the rash resolves, resume deferasirox at 50% of the subject's last dose, If the rash does not recur, increase dose back to 100% of the subject's dose after 2 weeks.

For a severe rash (distressing symptoms requiring discontinuation and/or systemic steroids), discontinue treatment until resolution of rash. Once the rash has resolved, resume at 50% of subject's dose. If necessary, a brief course of oral steroids may be given concurrently with resumption of deferasirox. If the rash does not recur, increase by steps of 3.5 mg/kg day deferasirox FCT every 2 weeks until the subject's last dose is achieved.

Rare cases of erythema multiforme (EM) have been reported during deferasirox treatment. Cases if suspected EM must be reported and DFX dose adjusted in accordance with the above recommendations for severe rash.

If rash recurs, study drug may be discontinued if the investigator believes that is in the best interest of the patient.

6.3.1.7 Increased liver enzyme levels

If there is a persistent and progressive increase in serum transaminase levels (ALT/AST) that cannot be attributed to other causes, deferasirox must be interrupted. Once the cause of the liver function test abnormalities has been identified, or after a return to normal levels, cautious re-initiation of deferasirox treatment at a lower dose followed by gradual dose escalation may be considered. In cases of a second rise in serum transaminase levels, the investigator should contact Novartis. Refer to table 6.4 for further modification, interruption guidance.

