6.3 Dose modifications

6.3.1 Dose modification and dose delay

For patients who do not tolerate the protocol-specified dosing schedule, dose interruptions and/or reductions are either recommended or mandated in order to allow patients to continue the study treatment.

These dose modifications are summarized in [Table 6-4](#). Deviations to mandatory dose interruptions and/or reductions are not allowed. Permanent treatment discontinuation is mandatory for specific events indicated as such in [Table 6-4](#) or listed in [Section 7.1.5](#).

These dose changes must be recorded on the Dosage Administration Record CRF.

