6.3.1.12 Gastrointestinal disturbances

Some basic recommendations, based on practical experience, can be made to guide investigators in managing subjects who experience diarrhea.

At the first sign of diarrhea, consider anti-diarrhea medication such as loperamide.

Remind the subject to discontinue any laxative preparations or stool softeners.

Eat small, frequent meals. Determine if the subject is lactose intolerant. Note that deferasirox FCT does not contain lactose. Remind the subject to drink an adequate amount of clear liquid per day.

Patients with GI symptoms (including abdominal pain, nausea, vomiting, and diarrhea) and/or patients who are unable to tolerate once a day study drug dosing, the following treatment management steps are recommended in the order specified below:

- Change the timing of study drug administration from morning to evening, and in addition, try using an anti-diarrheal agent for 2 days in case of diarrhea
- If symptoms still continue, try administering the daily dose as a split dose twice daily.

[figure not shown]
Once symptoms resolve, twice daily dosing should be switched back to once daily.

Do not split dose if only prescribing one tablet per day.

- Should the GI issues persist, study drug may be discontinued if the investigator believes it is in the best interest of the patient.

Table 6-4 Criteria for dose reduction / interruption and re-initiation of deferasirox treatment for adverse drug reactions

Recommended dose modifications for deferasirox	
Body weight	
Increase/decrease of weight by >10% compared to baseline weight or body weight at last dose adjustment due to change in patient's body weight	
Dose of study medication needs to be adapted using Deferasirox FCT Weight Dose Table
 
Dose adjustment needed for Weight changes >10% compared to baseline weight or if there is a change in patient's body weight since last dose adjustment.
 
Smaller variations in body weight (<10%) during study, do not require dose adjustments. In this case, baseline body weight can be used to calculate correct dose.

Investigations (Renal)	
Serum creatinine and/or creatinine clearance	
Single increase in serum creatinine $\geq 33\%$	Maintain dose level and repeat the assessment at next visit as clinically indicated

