Single serum creatinine increase $\geq 33\%$ above baseline value and $> \text{ULN}$	
Deferasirox dose reduction by 7 mg/kg/day for the FCT is necessary.
 
If after dose reduction, resolution of serum creatinine occurs (<33%) and within normal limits, dose can be re-escalated to 100% of the last dose.
 
If increase in serum creatinine recurs again within 2 months according to guidelines above, therapy needs to be reduced to 50% of the last dose
 
After 2 months, if the serum creatinine increase does not recur, study medication may be re-escalated to 100% of the last dose depending on the clinical judgement of the investigator.
 
If after an initial dose reduction, a progressive increase in serum creatinine beyond the ULN is observed, or SCr increases re-occur repeatedly at adequate dose, a treatment interruption is recommended.
 
After a treatment interruption, if serum creatinine falls below the age-appropriate ULN on two consecutive visits, it is recommended to resume therapy at 50% of the last dose, and after 1 month, if the serum creatinine increase does not recur, study medication can be returned to 100% of the last dose (including body weight adjustment if required) depending on the clinical judgement of the investigator.

Patients who met the eligibility criteria and who experience a renal function decrease $< \text{LLN}$ ($\text{CrCl} < 90 \text{ml/min}$) at 2 consecutive visits	
If decrease cannot be attributed to other causes, DFX must be dose reduced by 7mg/kg/day.
 
If after dose reduction the renal function increases $>$

Recommended dose modifications for deferasirox

LLN (CrCl >90ml/min), dose may be re-escalated to the last daily dose prior dose reduction depending on the clinical judgement of the investigator.
If after dose reduction the renal function remains <LLN (CrCl <90ml/min), treatment must be interrupted.
Treatment may be reinitiated depending on the clinical judgement of the investigator.
If creatinine clearance falls below 60ml/min study treatment must be discontinued.

Investigations (Hepatic)**Isolated direct (conjugated) Bilirubin elevation**

> ULN – 1.5 x ULN

Maintain dose level

> 1.5 - 3.0 x ULN

Omit dose with weekly monitoring of LFTs, or more frequently if clinically indicated, until resolved to \leq 1.5 x ULN.

If resolved in \leq 14 days, then maintain dose level

If resolved in > 14 days, then dose reduction of 3.5 or 7 mg/kg/day for deferasirox FCT.

> 3.0 - 10.0 x ULN

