Omit dose with weekly monitoring of LFTs, or more frequently if clinically indicated, until resolved to \leq 1.5 x ULN.

If resolved in \leq 14 days, then dose reduction of 3.5 or 7 mg/kg/day for deferasirox FCT

If resolved in > 14 days, then discontinue patient from study drug treatment. The patient needs to be monitored weekly (including LFTs), or more frequently if clinically indicated until TBIL have resolved to baseline or stabilization. Please refer to section 6.3.3 for additional details on follow-up.

> 10.0 x ULN*

Discontinue patient from study drug treatment
The patient needs to be monitored weekly (including LFTs), or more frequently if clinically indicated, until TBIL have resolved to baseline or stabilization. Please refer to section 6.3.3 for additional details on follow-up.

AST or ALT elevation

> ULN - 3.0 x ULN

Maintain dose level

> 3.0 - 5.0 x ULN

(For patients with baseline value \leq 3.0 x ULN)

(For patients with baseline value > 3.0 -5.0 x ULN)

> 5.0 - 10.0 x ULN

(For patients with baseline value > 3.0 -5.0 x ULN)

> 5.0 - 10.0 x ULN

(For patients with baseline value \leq 3.0 x ULN)

> 10.0 - 20.0 x ULN

Maintain dose level.

Repeat LFTs as soon as possible, preferably within 48-72 hours from awareness of the abnormal results; if abnormal lab values are confirmed upon the repeat test, then monitor LFTs weekly, or more frequently if clinically indicated, until resolved to $\leq 3.0 \times$ ULN. Please refer to section 6.3.3 for additional details on follow-up.

Maintain dose level.

Omit dose.

Repeat LFTs as soon as possible, preferably within 48- 72 hours from awareness of the abnormal results; monitor LFTs weekly, or more frequently if clinically indicated, until resolved to $\leq 3.0 \times$ ULN
If resolved in ≤ 14 days, maintain dose level
If resolved in > 14 days, then dose reduction of 3.5 or 7 mg/kg/day for deferasirox FCT.

Omit dose.

Repeat LFTs as soon as possible, preferably within 48-

Confidential

6 Protocol No.

Page 40

Recommended dose modifications for deferasirox**> 20.0 x ULN**

(For patients with baseline value > 3.0 -5.0 x ULN)

72 hours from awareness of the abnormal results; monitor LFTs weekly, or more frequently if clinically indicated, until resolved to \leq baseline. Then dose reduction of 3.5 or 7 mg/kg/day for deferasirox FCT.

Discontinue patient from study drug treatment

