Repeat LFTs as soon as possible, preferably within 48-72 hours from awareness of the abnormal results; monitor LFTs weekly, or more frequently if clinically indicated, until resolved to baseline or stabilization. Please refer to section 6.3.3 for additional details on follow-up of toxicities.

Combined elevations of AST or ALT and total bilirubin

For patients with normal baseline ALT or AST or total bilirubin value:

AST or ALT >3.0xULN combined with total bilirubin >2.0 x ULN without evidence of cholestasis

OR

[AST or ALT>2x baseline AND > 3.0 xULN] OR [AST or ALT > 8.0 xULN], whichever is lower, combined with [total bilirubin >2x baseline AND >2.0 xULN]

Interrupt study treatment.

Permanently discontinue patient from study drug treatment if no other plausible explanation can be found for the combined increase.

Repeat as soon as possible, preferably within 48 hours from awareness of the abnormal results, then with weekly monitoring of LFTs, or more frequently if clinically indicated, until AST, ALT, or bilirubin have resolved to baseline or stabilization.

Please refer to section 6.3.3 for additional details on follow-up of toxicities.

Hepatic impairment

Moderate hepatic impairment (Child- Pugh Class B

The study medication will be interrupted and patient monitored. If liver disease prognosis improves, deferasirox can be reintroduced at 7 mg/kg/day for FCT or 50% of previous dose, whichever is less. While monitoring continues, dose may be increased by 3.5 mg/kg/day for FCT every 2 weeks, to a maximum of 50% of patient's previous dose if the investigator determines that dose increase is in the best interest of the patient. Study medication must be used with caution in such patients.

In patients who develop severe hepatic impairment (Child-Pugh Class C) during the study

Study medication must be discontinued.

Other recommended dose modifications**Changes in Serum Ferritin**

500 – 1000 ng/mL

The dose of deferasirox FCT should be adjusted as necessary every 3 months based on the trends in serum ferritin and investigator's judgement.

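### Table 6-4 tells sites to maintain the dose for low-grade ALT/AST rises, with no exception for the persistent, progressive, unexplained rise that Section 6.3.1.7 says must lead to interruption

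*Protocol*

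**What the plan says.** Protocol Section 6.3.1.7 states: "If there is a persistent and progressive increase in serum transaminase levels (ALT/AST) that cannot be attributed to other causes, deferasirox must be interrupted". It sets no minimum level, and it closes by sending the reader on: "Refer to table 6.4 for further modification, interruption guidance".

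Table 6-4 sorts isolated AST/ALT elevations by ULN band and baseline value. For >ULN to 3.0 x ULN the only instruction is to maintain the dose. The action that appears to belong to >3.0 to 5.0 x ULN with baseline at or below 3.0 x ULN is also to maintain the dose, with a repeat test: "if abnormal lab values are confirmed upon the repeat test, then monitor LFTs weekly". No AST/ALT row mentions persistence, progression or cause.

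On how text and table relate, Section 6.3.1 says of the dose changes: "These dose modifications are summarized in" Table 6-4. It then adds: "Deviations to mandatory dose interruptions and/or reductions are not allowed". The table itself is headed "Recommended dose modifications for deferasirox".

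**The concern.** The text rule is triggered by a trend at any level. The table rule is triggered by a level whatever the trend. In the lowest band, and probably the next, they give opposite instructions for the same child. Section 6.3.1.7 itself directs the reader to the table, where the applicable row says to carry on dosing.

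A site working from the table would keep a child aged 2 to under 6 on drug against an interruption that Section 6.3.1 treats as binding. A site working from the text would stop. The same laboratory course would then be handled differently across sites, with three consequences:

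- **Hepatic safety:** exposure continues during an unexplained rise.
- **Dose summaries:** interruption counts and reasons (SAP 2.6.4) would partly reflect which page a site used.
- **AE status:** under Protocol 8.1.2.1, a dose hold required by the protocol makes the laboratory abnormality an AE, so counts could differ too.

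**Working it through.** **1. The two instructions side by side.** Take an illustrative ALT course of 1.2, then 1.8, then 2.6 x ULN, with no other cause found and the investigator judging it persistent and progressive. The values are assumed.

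| Source | Trigger | Instruction |
|---|---|---|
| Section 6.3.1.7 | Persistent, progressive, unexplained rise at any level | Interrupt (mandatory) |
| Table 6-4, >ULN to 3.0 x ULN | Value within the band | Maintain dose |

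All three values fall in the one row, and both instructions cannot be followed. A child may start in this band, because exclusion criterion 7 applies only above 2.5 x ULN.

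**2. How secure the table reading is.** In the lowest row the action is printed directly under its band, so the reading is firm. After that row the available text separates bands from actions, giving six band/baseline conditions and five actions. Both conditions for >3.0 to 5.0 x ULN come first in the list, and the first two actions both maintain the dose before any omission appears. That makes a maintain-dose instruction for this band probable, not certain.

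**3. Whether another rule closes the gap.** The combined-elevation row of Table 6-4 and the drug-induced liver injury rule in Section 6.3.3.1 both require bilirubin to rise as well. The Child-Pugh rows concern hepatic impairment. None covers an isolated progressive ALT/AST rise.

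**4. Whether the table usually carries the mandatory stops.** Sections 6.3.1.2 to 6.3.1.11 contain seven stop rules worded with 'must'.

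| Stop rule in the text | Section | Stop in Table 6-4? |
|---|---|---|
| CrCl still <90 mL/min after reduction | 6.3.1.3 | Yes, 'must' |
| CrCl <60 mL/min | 6.3.1.3 | Yes, 'must' |
| UPCR >1.0 mg/mg | 6.3.1.5 | Yes, without 'must' |
| Severe skin reaction | 6.3.1.6.1 | Yes, 'must' |
| ALT/AST trend | 6.3.1.7 | **No** |
| Child-Pugh C | 6.3.1.8 | Yes, 'must' |
| Severe hypersensitivity | 6.3.1.10 | Yes, 'should' |

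Six of the seven have a stop in the table, four of them in 'must' wording; examples are "If after dose reduction the renal function remains <LLN (CrCl <90ml/min), treatment must be interrupted" and "Study medication must be discontinued". Only the transaminase trend rule is absent.

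**5. Size.** The documents do not report how often rises were persistent, progressive and unexplained, so only any suspected rise can be scaled. Inputs, all for the observational dispersible-tablet study in this age group:

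- Suspected ALT increase 21.1%, suspected AST increase 11.9%, ALT >5 x ULN 4.3% (Protocol 1.2.1.2).
- Exposure mean 44.1 months, median 59.9 months (Protocol 1.2).
- 40 children (Protocol 10.8) over 24 weeks = 168/30.4375 = 5.52 months.

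Assuming a constant rate, p24 = 1 − exp[ln(1 − p) × 5.52/d], multiplied by 40, with d the exposure in months. For ALT with d = 44.1: 1 − exp[ln(0.789) × 5.52/44.1] = 2.92%, and 0.0292 × 40 = 1.17.

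| Event | d = 44.1 | d = 59.9 |
|---|---|---|
| ALT increase | 2.92% = 1.17 | 2.16% = 0.86 |
| AST increase | 1.57% = 0.63 | 1.16% = 0.46 |
| Either, no child with both (sum) | 1.80 | 1.32 |
| ALT, hazard doubled | 5.76% = 2.30 | 4.27% = 1.71 |
| AST, hazard doubled | 3.12% = 1.25 | 2.31% = 0.92 |
| Either, hazard doubled, no overlap | 3.55 | 2.63 |
| ALT >5 x ULN (outside the conflict) | 0.55% = 0.22 | 0.40% = 0.16 |

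If every AST rise occurred in a child with an ALT rise, the count for either enzyme equals the ALT count, 0.86 to 1.17. The doubled hazard is an assumption allowing for early clustering; the documents give no figure for it.

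**The case against.** The strongest reply is that only one action complies. Section 6.3.1 protects mandatory interruptions, and maintaining a dose is not one. Section 6.1.4 describes Table 6-4 as giving further detail to Section 6.3, Section 6.3.1.7 also cites the table for further guidance, and the table is headed as recommendations. A rule on level and a rule on trend can coexist. This stands as far as it goes: it shows how the conflict ought to be resolved. It does not put the resolution in the row a site reads, and if the text governs, the row leads the site into a prohibited deviation.

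A second reply is that a summary may omit things, and the table departs from the text elsewhere. The UPCR stop needs two samples in Section 6.3.1.5 but one in the table, the hypersensitivity stop is worded more weakly, and split dosing for gastrointestinal symptoms is missing. These differences are real, and the six carried-over stops are not identical copies. But the two altered stops still tell the site to stop; the transaminase row tells it to continue.

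Third, the trigger words are undefined and excluding other causes is a matter of judgement, particularly where Protocol 1.2.1.2 describes background liver damage from iron overload and viral hepatitis. This is fair, and it limits how often the conflict would be unmistakable.

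Fourth, the practical stakes are limited. The investigator may stop drug on clinical grounds (7.1.5), unscheduled tests are allowed (7.1.9), and a rise judged clinically significant is an AE even without a hold. All true. Discretion to stop, however, is not the same as an instruction to stop.

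**Conclusion.** The concern holds. For >ULN to 3.0 x ULN, Table 6-4 contradicts a mandatory interruption in Section 6.3.1.7. For >3.0 to 5.0 x ULN it very probably does too, subject to the broken table layout.

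The number of children is small: 0.9 to 1.8 of 40 with any suspected ALT or AST increase at a constant rate, or 1.7 to 3.6 if the hazard is doubled. These are ceilings under their assumptions, because only a subset would be persistent, progressive and unexplained. They also rest on a different formulation and on exposure far longer than 24 weeks.

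The primary analysis and sample size are untouched. Rises at or below 5 x ULN would still be visible in the SAP's shift tables, change summaries, box plots and listings (SAP 2.11 and 2.11.4). The matter should be fixed because it concerns patient safety and consistent conduct across sites.

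**What to change.** Add to each maintain-dose AST/ALT row of Table 6-4: *unless the rise is persistent, progressive and unexplained, in which case interrupt per 6.3.1.7*. Tell sites by letter.

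The cost is one line in the table and the letter, with no new visit, test or patient. The downside is possibly a few more interruptions, which Section 6.3.1.7 already requires. The line does not define persistent or progressive, so some judgement between sites would remain.

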6.3.1.8 Hepatic Impairment

In subjects with moderate hepatic impairment (Child-Pugh Class B), put the study medication on hold and monitor the patient for total bilirubin, serum albumin, prothrombin time, International Normalized Ratio (INR), ascites and hepatic encephalopathy. If liver disease prognosis improves, study medication may be reintroduced at 7 mg/kg/day for FCT or 50% of previous dose, whichever is less.

While monitoring continues, the dose may be increased by 3.5 mg/kg/day for FCT every 2 weeks to a maximum of 50% of the patient's previous dose if the investigator determines that dose increase is in the best interest of the patient.

In subjects who develop severe hepatic impairment (Child-Pugh Class C) during the study, deferasirox must be discontinued.

6.3.1.9 Dose modification criteria for auditory (decreased hearing) and ocular (lens opacities) disturbances

Auditory (decreased hearing) and ocular (lens opacities) disturbances have been reported with deferasirox treatment. Auditory testing will be performed at screening visit 1 before the start of deferasirox treatment and at end of treatment and is permitted through the remainder of the study at the discretion of the Investigator based on subject's reporting of symptoms. Ocular testing will be performed at screening before the start of deferasirox treatment and at end of treatment and is permitted through the remainder of the study at the discretion of the Investigator based on the subject's reporting of symptoms. If auditory or ocular disturbances are noted, dose reduction or interruption may be considered and a repeated testing performed as per investigator's judgement.

6.3.1.10 Dose modification criteria for hypersensitivity reactions

Cases of serious hypersensitivity reactions (such as anaphylaxis and angioedema) have been reported in patients receiving deferasirox, with the onset of the reaction occurring in the majority of cases within the first month of treatment. If reactions are severe, deferasirox must be discontinued. Deferasirox must not be reintroduced in patients who have experienced previous hypersensitivity reactions on deferasirox due to the risk of anaphylactic shock.

6.3.1.11 Dose modification criteria for cytopenias

There have been reports (both post-marketing and from clinical trials) of cytopenias in patients treated with deferasirox. Most of these patients had pre-existing hematological disorders that are frequently associated with bone marrow failure. The relationship of these episodes to treatment with deferasirox is uncertain. In line with the standard clinical management of such hematological disorders, blood counts should be monitored regularly. Dose interruption of treatment with deferasirox should be considered in patients who develop unexplained cytopenias. Reintroduction of therapy with deferasirox may be considered once the cause of cytopenia has been identified.

6.3.1.12 Gastrointestinal disturbances

Some basic recommendations, based on practical experience, can be made to guide investigators in managing subjects who experience diarrhea.

At the first sign of diarrhea, consider anti-diarrhea medication such as loperamide.

Remind the subject to discontinue any laxative preparations or stool softeners.

Eat small, frequent meals. Determine if the subject is lactose intolerant. Note that deferasirox FCT does not contain lactose. Remind the subject to drink an adequate amount of clear liquid per day.

Patients with GI symptoms (including abdominal pain, nausea, vomiting, and diarrhea) and/or patients who are unable to tolerate once a day study drug dosing, the following treatment management steps are recommended in the order specified below:

- Change the timing of study drug administration from morning to evening, and in addition, try using an anti-diarrheal agent for 2 days in case of diarrhea
- If symptoms still continue, try administering the daily dose as a split dose twice daily.

[figure not shown]
Once symptoms resolve, twice daily dosing should be switched back to once daily.

Do not split dose if only prescribing one tablet per day.

- Should the GI issues persist, study drug may be discontinued if the investigator believes it is in the best interest of the patient.

Table 6-4 Criteria for dose reduction / interruption and re-initiation of deferasirox treatment for adverse drug reactions

Recommended dose modifications for deferasirox	
Body weight	
Increase/decrease of weight by >10% compared to baseline weight or body weight at last dose adjustment due to change in patient's body weight	
Dose of study medication needs to be adapted using Deferasirox FCT Weight Dose Table
 
Dose adjustment needed for Weight changes >10% compared to baseline weight or if there is a change in patient's body weight since last dose adjustment.
 
Smaller variations in body weight (<10%) during study, do not require dose adjustments. In this case, baseline body weight can be used to calculate correct dose.

Investigations (Renal)	
Serum creatinine and/or creatinine clearance	
Single increase in serum creatinine $\geq 33\%$	Maintain dose level and repeat the assessment at next visit as clinically indicated
Single serum creatinine increase $\geq 33\%$ above baseline value and $> \text{ULN}$	
Deferasirox dose reduction by 7 mg/kg/day for the FCT is necessary.
 
If after dose reduction, resolution of serum creatinine occurs (<33%) and within normal limits, dose can be re-escalated to 100% of the last dose.
 
If increase in serum creatinine recurs again within 2 months according to guidelines above, therapy needs to be reduced to 50% of the last dose
 
After 2 months, if the serum creatinine increase does not recur, study medication may be re-escalated to 100% of the last dose depending on the clinical judgement of the investigator.
 
If after an initial dose reduction, a progressive increase in serum creatinine beyond the ULN is observed, or SCr increases re-occur repeatedly at adequate dose, a treatment interruption is recommended.
 
After a treatment interruption, if serum creatinine falls below the age-appropriate ULN on two consecutive visits, it is recommended to resume therapy at 50% of the last dose, and after 1 month, if the serum creatinine increase does not recur, study medication can be returned to 100% of the last dose (including body weight adjustment if required) depending on the clinical judgement of the investigator.

Patients who met the eligibility criteria and who experience a renal function decrease $< \text{LLN}$ ($\text{CrCl} < 90 \text{ml/min}$) at 2 consecutive visits	
If decrease cannot be attributed to other causes, DFX must be dose reduced by 7mg/kg/day.
 
If after dose reduction the renal function increases $>$

Recommended dose modifications for deferasirox

LLN (CrCl >90ml/min), dose may be re-escalated to the last daily dose prior dose reduction depending on the clinical judgement of the investigator.
If after dose reduction the renal function remains <LLN (CrCl <90ml/min), treatment must be interrupted.
Treatment may be reinitiated depending on the clinical judgement of the investigator.
If creatinine clearance falls below 60ml/min study treatment must be discontinued.

Investigations (Hepatic)**Isolated direct (conjugated) Bilirubin elevation**

> ULN – 1.5 x ULN

Maintain dose level

> 1.5 - 3.0 x ULN

Omit dose with weekly monitoring of LFTs, or more frequently if clinically indicated, until resolved to \leq 1.5 x ULN.

If resolved in \leq 14 days, then maintain dose level

If resolved in > 14 days, then dose reduction of 3.5 or 7 mg/kg/day for deferasirox FCT.

> 3.0 - 10.0 x ULN

Omit dose with weekly monitoring of LFTs, or more frequently if clinically indicated, until resolved to \leq 1.5 x ULN.

If resolved in \leq 14 days, then dose reduction of 3.5 or 7 mg/kg/day for deferasirox FCT

If resolved in > 14 days, then discontinue patient from study drug treatment. The patient needs to be monitored weekly (including LFTs), or more frequently if clinically indicated until TBIL have resolved to baseline or stabilization. Please refer to section 6.3.3 for additional details on follow-up.

> 10.0 x ULN*

Discontinue patient from study drug treatment
The patient needs to be monitored weekly (including LFTs), or more frequently if clinically indicated, until TBIL have resolved to baseline or stabilization. Please refer to section 6.3.3 for additional details on follow-up.

AST or ALT elevation

> ULN - 3.0 x ULN

Maintain dose level

> 3.0 - 5.0 x ULN

(For patients with baseline value \leq 3.0 x ULN)

(For patients with baseline value > 3.0 -5.0 x ULN)

> 5.0 - 10.0 x ULN

(For patients with baseline value > 3.0 -5.0 x ULN)

> 5.0 - 10.0 x ULN

(For patients with baseline value \leq 3.0 x ULN)

> 10.0 - 20.0 x ULN

Maintain dose level.

Repeat LFTs as soon as possible, preferably within 48-72 hours from awareness of the abnormal results; if abnormal lab values are confirmed upon the repeat test, then monitor LFTs weekly, or more frequently if clinically indicated, until resolved to $\leq 3.0 \times$ ULN. Please refer to section 6.3.3 for additional details on follow-up.

Maintain dose level.

Omit dose.

Repeat LFTs as soon as possible, preferably within 48- 72 hours from awareness of the abnormal results; monitor LFTs weekly, or more frequently if clinically indicated, until resolved to $\leq 3.0 \times$ ULN
If resolved in ≤ 14 days, maintain dose level
If resolved in > 14 days, then dose reduction of 3.5 or 7 mg/kg/day for deferasirox FCT.

Omit dose.

Repeat LFTs as soon as possible, preferably within 48-

Confidential

6 Protocol No.

Page 40

Recommended dose modifications for deferasirox**> 20.0 x ULN**

(For patients with baseline value > 3.0 -5.0 x ULN)

72 hours from awareness of the abnormal results; monitor LFTs weekly, or more frequently if clinically indicated, until resolved to \leq baseline. Then dose reduction of 3.5 or 7 mg/kg/day for deferasirox FCT.

Discontinue patient from study drug treatment

Repeat LFTs as soon as possible, preferably within 48-72 hours from awareness of the abnormal results; monitor LFTs weekly, or more frequently if clinically indicated, until resolved to baseline or stabilization. Please refer to section 6.3.3 for additional details on follow-up of toxicities.

Combined elevations of AST or ALT and total bilirubin

For patients with normal baseline ALT or AST or total bilirubin value:

AST or ALT >3.0xULN combined with total bilirubin >2.0 x ULN without evidence of cholestasis

OR

[AST or ALT>2x baseline AND > 3.0 xULN] OR [AST or ALT > 8.0 xULN], whichever is lower, combined with [total bilirubin >2x baseline AND >2.0 xULN]

Interrupt study treatment.

Permanently discontinue patient from study drug treatment if no other plausible explanation can be found for the combined increase.

Repeat as soon as possible, preferably within 48 hours from awareness of the abnormal results, then with weekly monitoring of LFTs, or more frequently if clinically indicated, until AST, ALT, or bilirubin have resolved to baseline or stabilization.

Please refer to section 6.3.3 for additional details on follow-up of toxicities.

Hepatic impairment

Moderate hepatic impairment (Child- Pugh Class B

The study medication will be interrupted and patient monitored. If liver disease prognosis improves, deferasirox can be reintroduced at 7 mg/kg/day for FCT or 50% of previous dose, whichever is less. While monitoring continues, dose may be increased by 3.5 mg/kg/day for FCT every 2 weeks, to a maximum of 50% of patient's previous dose if the investigator determines that dose increase is in the best interest of the patient. Study medication must be used with caution in such patients.

In patients who develop severe hepatic impairment (Child-Pugh Class C) during the study

Study medication must be discontinued.

Other recommended dose modifications**Changes in Serum Ferritin**

500 – 1000 ng/mL

The dose of deferasirox FCT should be adjusted as necessary every 3 months based on the trends in serum ferritin and investigator's judgement.

ICT naïve patients can adapt dose after 4 weeks on study. Dose adjustments for deferasirox FCT 3.5 mg or 7 mg/kg/day are to be tailored to the individual patient's response and the therapeutic goal of (reduction of iron burden). In patients not adequately controlled with deferasirox FCT doses of 21 mg/kg/day, doses of up to 28 mg/kg/day may be considered. The starting dose and the dose adjustment considerations must take into account that the therapeutic goal is reduction of iron burden (as opposed to maintenance of iron burden). Doses above 28 mg of deferasirox FCT

Recommended dose modifications for deferasirox

< 500 ng/ml	deferasirox FCT are required to maintain serum ferritin levels within the target range. Interruption of study treatment is required until serum ferritin rises above 500 ng/mL
Changes in urine protein/creatinine ratio	
> 0.5 (mg/mg) in two consecutive non- first void urine samples (a minimum of 48h apart), if all other causes of proteinuria have been excluded.	For patients who develop proteinuria or a worsening of pre-existing proteinuria at any visit, urine samples should be collected and assessed by the laboratory. In case of a single increase of the urinary protein/creatinine ratio the assessment should be repeated at the next visit. Deferasirox FCT dose reduction by 50% When resolution of UPCR (<0.5mg/mg) at the next study visit, dose can be resumed again at 100% If increase in UPCR >0.5mg/mg recurs again within 2 months after initial increase, therapy needs to be reduced to 50% of the last dose. If increase in UPCR does not recur after 2 months at reduced dose (50%), study medication can be returned to 100% of the last dose. Interrupt study treatment. When resolution of increase in UPCR (<0.5mg/mg) at the next study visit, dose can be resumed again at 50% of the last dose. If increase in UPCR does not recur after 1 month at reduced dose (50%), study medication can be returned to 100% of the last dose. Should proteinuria persist, study treatment may be discontinued if the investigator believes it is in the best interest of the patient. Novartis may be contacted by the investigator to discuss dosing options if the investigator so desires. Dose adjustment will be based on laboratory results.
> 1.0 (mg/mg) in one single non-first void urine samples.	
Severe skin reactions	
Severe skin reactions, including Stevens-Johnson syndrome (SJS), Toxic epidermal necrolysis (TEN), DRESS	Must be reported if occurs during Exjade therapy. If SJS ,TEN, DRESS is suspected, study treatment must be immediately discontinued and not be reintroduced
Skin Rash (other than SJS, TEN, DRESS)	
For skin rash of mild/moderate severity (defined as those causing minimal symptoms which require no or minimal supportive treatment)	Study drug should be continued without dose adjustment. The skin rash may resolve spontaneously without further intervention. If the rash persists for >1 week or becomes more severe, treatment with study drug will be interrupted. After the rash resolves, resume study drug at 50% of patient's last dose. If the rash does not recur, increase dose back to 100% of patients dose after 2 weeks. Discontinue treatment until resolution of rash. Once the rash has resolved, resume at 50% of patient's dose. If necessary, a brief course of oral steroids may be given concurrently with resumption of study drug. If the rash does not recur, increase by steps of 3.5 mg/kg/day for deferasirox FCT every 2 weeks until patient's last dose is achieved. If the rash recurs, study treatment may be discontinued if the investigator believes that it is in the best interest
Severe rash (distressing symptoms requiring discontinuation and/or systemic steroids)	

Recommended dose modifications for deferasirox

of the patient.

Novartis may be contacted by the investigator to discuss dosing options if the investigator so desires

Dose modification criteria for auditory and ocular disturbances

Auditory (decreased hearing) and ocular (lens opacities) disturbances have been reported with deferasirox treatment.

Auditory and ophthalmic testing is required before the start of deferasirox treatment.

If disturbances are noted dose reduction or interruption may be considered and a repeated testing performed as per investigator's judgment.

Dose modification criteria for hypersensitivity reactions

Cases of serious hypersensitivity reactions (such as anaphylaxis and angioedema) have been reported in patients receiving deferasirox, with the onset of the reaction occurring in the majority of cases within the first month of treatment.

If reactions are severe, deferasirox should be discontinued and appropriate medical intervention instituted.

Deferasirox should not be reintroduced in patients who have experienced previous hypersensitivity reactions on deferasirox due to the risk of anaphylactic shock

Dose modification criteria for cytopenias

Unexpected Cytopenias

There have been post-marketing reports (both spontaneous and from clinical trials) of cytopenias in patients treated with deferasirox. Most of these patients had pre-existing hematological disorders that are frequently associated with bone marrow failure. The relationship of these episodes to treatment with deferasirox is uncertain. In line with the standard clinical management of such hematological disorders, blood counts should be monitored regularly. Dose interruption of treatment with deferasirox should be considered in patients who develop unexplained cytopenia. Reintroduction of therapy with deferasirox may be considered (as per investigator decision), once the cause of the cytopenia has been identified.

Gastrointestinal disturbances

Gastrointestinal issues (including diarrhea, constipation, nausea, vomiting and abdominal pain)

Some basic recommendations, based on practical experience, can be made to guide physicians in managing patients who experience diarrhea.

At the first sign of diarrhea, consider anti-diarrheal medication such as loperamide. Remind the patient to discontinue any laxative preparations or stool softeners they may be taking and to eat small, frequent meals. Determine if the patient is lactose intolerant. Monitor fluid intake and adapt as necessary according to body weight.

Should the gastrointestinal issues (including diarrhea, constipation, nausea, vomiting and abdominal pain) persist, study drug may be discontinued if the investigator believes it is in the best interest of the patient.

Novartis may be contacted by the investigator to discuss dosing options if the investigator so desires.

